## **10. Data Management**

Generally, data will be collected on CRFs and transferred to the database, which is maintained by the sponsor. Data (seizure times) from the EDDI are during the monitoring saved on SD-cards. When a patient is finished, all data in 8.6.1 is typed down in the CRF and sent to the sponsor. The SD-card is shipped to the Device Manufacturer, who will read out the seizure detection times, and sent them to the sponsor, who will collect them in a separate CRF. The sponsor is responsible for collecting all data in the two CRFs, and furthermore locks these two documents. A copy of the final two CRFs will be handed over to the Device Manufacturer.

Sponsor will keep data for 10 years.

#### 10.1 Data analysis

The data analysis will be performed by the principal investigator. The sensitivity and specificity of the device will be calculated. Furthermore the specificity will be calculated explicitly during night time.

For each false positive the EEG and video should be checked to see if there is an explanation for the false alarming.

Also for each GTC seizure that is registered by the alarm the latency should be calculated from the onset of the tonic phase of the GTC seizure.

For the patients with PNES it should be calculated how many of the seizures are registered by the alarm. The number is expected to be 0.

## **11.Amendments to the CIP**

Any variation in procedure from that specified in the Clinical Investigation Plan (CIP) may lead to the results of the Investigation being questioned and in some cases rejected. Any proposed CIP changes will be documented in a CIP amendment and this will be submitted to the Research Ethics Committee (REC) for approval prior to implementation.

## 12. Deviations from clinical investigation plan

Deviations from the CIP are not permissible (except in an emergency).

Any deviations are to be documented in the final Investigational Report. Under emergency circumstances, deviations from the CIP to protect the rights, safety and well-being of human subjects may proceed without prior approval of the sponsor and the EC/Regulatory authorities. Such deviations shall be documented to the sponsor and the EC as soon as possible and may cause amendment to the CIP.

## **13. Device accountability**

Accountability of the device and related supplies will be kept by IctalCare and the investigational site(s). An accurate, timely record for the disposition of all devices and related supplies must be maintained as follows:

- Identification of the subject to whom which device(s) were allocated and used by
- The date(s) and quantity of device(s) and related supplies used by the subject
- The product lot/batch numbers

Records/tracks will be documented.

## **14. Statements of compliance**

The investigation will be conducted in accordance with the ethical principles contained in the Declaration of Helsinki, the requirements of the Ethics Committees, and the European Medical Device Directive, EN ISO 14155-1, EN ISO 14155-2 and the CIP.

#### 14.1 Approval of the ethics committee

The test will be reported to the local REC by the investigator(s).

#### 14.2 Approval of the Danish Health and Medicines Authority

The EDDI is CE marked, and an approval from the Danish Health and Medicines Authority is thereby not necessary.

#### **14.3 Danish Data Protection Agency**

During the investigation information on private relations regarding the patient will be stored and processed, thus it is to comply with the regulations put forth in the Act on Processing of Personal Data.

#### **15. Informed consent process**

Prior to any investigational related procedures the information for the patient and the declaration of consent (approved by the local REC) are provided to the patients by an investigator delegated to the task. The information is given both in writing and orally in a, to the patient, understandable language. The written consent will be collected.

The oral information must be provided in an undisturbed room. The patient should have plenty of time to ask questions and may bring a companion to the conversation, which he/she should be informed about prior to the talk. The written consent is given based on both the written and oral information and may further be provided after some time to consider the information.

The original written consent is stored by the investigator. A copy of the written consent is provided to the patient.

The patient may at any time and without any explanation withdraw the written consent and thus withdraw from the investigation. This will not have any affect for the patient in the present or later treatments.

#### Children

When a child or a young person under the age of 18 participates in the investigation, the written consent is obtained from each of the persons holding the custody. The persons holding the custody are informed about the investigation both orally and in writing.

The child or the young person will also receive oral information on the investigation. The information will be given by a person, who has the preconditions to inform a child or young person, so that it is told in a way suited the age of the patient.

Possible expressions by the child or young person will have influence in the extent where it is relevant.

If a patient aged 15-17 wishes to have the information in writing, written information will be provided in a language adjusted to the age of the patient.

When including under-aged patients in the investigation, it requires that both possessors of custody give their written consent. This is not the case, when one parent has authorized the other in decisions regarding the child's participation in investigations.

The consent will express the interest of the under-aged patient. If the under-aged patient protests against the investigation, orally or physically, the investigation cannot be accomplished.

If the under-aged patient turns 18 within the investigational period, a written consent is to be obtained from the patient before the investigation continues.

The consent will be written, dated and signed based on the received written and oral information. The consent will be given to the person responsible for the investigation or the one who have been given the responsibility of providing the oral information. This person will be directly associated to the investigation. Original written consents will be stored by the person in charge of the investigation, and the patient or the persons holding the custody will be given a copy of the attested consent.

#### Mentally retarded adults

In the investigation it is the guardian, or the closest relative and the practicing doctor, or alternatively the National board of Health, who will submit the deputy consent.

The deputy consent will be obtained in cases where the patient is unfit/unable to give the consent themselves. This includes that the person giving the deputy consent must be informed of the investigation both in written and orally.

The mentally retarded adult patients, who are unable to give a written consent, will be informed and involved in the conversation on the investigation in a suited extent, unless it is damaging for the patients. The patient's expressions will be ascribed value in the amount it is relevant.

Regarding the closest relative: A specific evaluation will define who the closest relative is. This may be the patient's spouse, relative in straight line or siblings. Dependent on the circumstances, foster children will

often be considered as the closest relative, especially when there is no spouse or children. In such cases other relatives, which are tightly bound to the patient, will be seen as close relatives. Both the family relation and the tightness of the bound are considered. The person submitting the deputy consent will know the patient very well and hold the patient's trust. Thus a very close friend is able to give the deputy consent in some cases.

Regarding the practicing doctor or health inspector: The deputy consent from the practicing doctor will be submitted based on the doctor's knowledge of the patient, or the doctor's ability to become familiar with the patient or the patient's health relation, compared to the information on the investigation. The deputy consent of the doctor will be obtained to secure extra protection of the mentally retarded adult. When the patient's doctor is absent, or the patients does not have a fixed doctor, the deputy consent must be submitted from the closest relative or the National Board of Health (health inspector). The practicing doctor or the National Board of Health will, because of his/her education ensure that the consent is handled such that the patient is not harmed. This will be based on the doctor's knowledge of the patient or the doctor's ability to become familiar with the health of the patient.

Regarding the guardian: The guardian will submit the deputy consent, if the person to attend the investigation is under personal guardianship. This requires that the guardianship contains the authority to provide consent regarding participation in trials.

The deputy consent will express the patient's interest and the patient will receive information adjusted to the comprehension ability of the patient. Regardless of deputy consent, the investigation will not be conducted if the patient resists. This does not have to be formulated orally, but may also be expressed physically.

The consent will be written, dated and signed based on the received information; written and orally. The consent will be given to the person responsible for the investigation or the one who have been given the responsibility of providing the oral information. This person will be directly associated to the investigation. Original written consents will be stored by the person in charge of the investigation, and the patient or the persons holding the custody will be given a copy of the attested consent.

## **16.** Adverse events, adverse device effects and device deficiencies

## 16.1 Adverse Event (AE)

Any untoward medical occurrence, unintended disease or injury or any untoward clinical signs (including an abnormal laboratory finding) in subjects, users or other persons whether or not related to the investigated medical device. This includes events related to the investigational device. This includes events related to the clinical investigation plan).

#### **16.2 Adverse Device Effect (ADE)**

AE related to the use of an investigational medical device. This includes any AE resulting from insufficiencies or inadequacies in the instructions for use, the deployment, the implantation, the installation, the operation, or any malfunction of the investigational medical device. This includes any event that is a result of a user error or intentional misuse.

#### **16.3 Device deficiency**

Inadequacy of a medical device related to its identity, quality, durability, reliability, safety or performance, such as malfunction, misuse or user error and inadequate labeling.

#### **16.4 Serious Adverse Device Effect (SADE)**

A **Serious Adverse Device Effect** is an Adverse Device Effect that has resulted in any of the consequences characteristic of a Serious Adverse Event (see 16.5). Added to that also **near-incidents** which are characterized by the fact that it would have led to above consequences if suitable action had not been taken or intervention had not been made or if circumstances had been less opportune.

#### 16.5 Serious Adverse Event (SAE)

AEs that resulted in one or more of the following:

- Death
- Life-threatening injury or illness
- Permanent impairment of a body structure or body function
- Patient Hospitalization or prolongation of existing hospitalization
- Medical or surgical intervention to avoid the above

Fetal death, a congenital abnormality or birth defect in the fetus or any other negative effect on the fetus.

A planned hospitalization for pre-existing condition, or a procedure required by the Clinical Investigation Plan, without a serious deterioration in health, is not considered to be a SAE.

#### 16.6 Unanticipated Serious Adverse Device Effect (USADE)

SADE which by its nature, incidence, severity or outcome has not been identified in the current version of the risk analysis report.

Anticipated: an effect which by its nature, incidence, severity or outcome has been previously identified in the risk analysis report.

#### **16.7 Reportable events**

The following events are considered reportable events

- any SAE or SADE,
- any Investigational Medical Device Deficiency (near-incident) that might have led to a SAE if
  - o suitable action had not been taken or
  - $\circ$  intervention had not been made or
  - if circumstances had been less fortunate
- any new findings/updates in relation to already reported events.

#### **16.8 Reporting timelines**

The principal investigator at the sites is responsible for reporting all SAE or SADE at their own site.

The present study is a clinical investigation of a medical device, thus events related to the patient's daily or acute medication will not be reported. Adverse effects suspected to be caused by the patient's medication

will be reported in accordance with the normal obligation to report for medical personnel, established by the DHMA. This means all critical or unexpected adverse effects from medications are reported. Besides it is the medical doctors duty to report known or none critical side effects in the first two years the product is on the market:

http://laegemiddelstyrelsen.dk/da/topics/bivirkninger-og-forsoeg/bivirkninger/meld-en-bivirkning-eller-utilsigtet-haendelse/mennesker/meld-en-bivirkning-ved-medicin-til-menne---e-blanket

All events, which are not related to the medication of the patient, will be reported in the CRF from the time of inclusion to withdrawal of the patient.

All SAEs occurring from accept of the participation to the end of the investigation will be reported by filling in and sending in the SADE form to the Medical monitor of the sponsor. This is to take place within 24 hours from the point where the investigator has encountered that the event fulfills the definition of a SAE/SADE. After this initial SAE/SADE report has been filled in, the investigator is obligated to proactively communicate further information on the patient's condition. All follow up information must be submitted to the Medical Monitor, as soon as it is available. If there appear SAEs/SADEs after the end of the investigation, they must be reported if they are related to the investigation.

The obligation to report is also present for SAE or SADE caused by inaccurate or insufficient results from diagnostic equipment, e.g. a wrong diagnosis, a delayed diagnosis, delayed treatment or wrong treatment.

The Medical Monitor of the Sponsor must ensure, that it is carefully evaluated whether the SAE or SADE are caused by the medical device during the trials or consequences of the use of the medical device.

The Medical Monitor of the Sponsor must ensure that all information on the SAE or SADE are registered and submitted to the REC as fast as possible and within 7 days after the Medical Monitor of sponsor has become aware of the event. However the deadline is 2 days, if the incident constitutes an imminent risk of further deaths, serious injury or illness and which requires immediate action to other patients / subjects, users, or others.

The information must be reported on "Notification Form for Serious Adverse Events or near-incidents with Medical Devices during the clinical investigation", which can be found on the DHMA:

http://medicinskudstyr.dk/da/menu/klinisk-afproevning/ansoegning-om-klinisk-afproevning-af-med--nskudstyr

Every report must be followed by comments on possible consequences of the investigation.

All Follow-up information to an already reported SAE/SADE is to follow the same requirements of and timelines for reporting as the initial report.

All events occurring during the trials must be reported in the final report of the investigation. This will also include events, which are not critical.

For all occurring deaths, reported at any time, all available autopsy reports and relevant medical reports must be sent by fax to the Medical Monitor (in a blinded format with no patient names).

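### Section 16.8 keeps events attributed to medication out of study reporting and the CRF, which conflicts with its own final-report rule and, unless the SAE rule is taken to override it, with the SAE reporting rules

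*Protocol*

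**What the plan says.** Section 16.8 reasons that the study concerns a device and concludes that events related to the patient's "daily or acute medication will not be reported". Suspected medication effects instead "will be reported in accordance with the normal obligation to report for medical personnel, established by the DHMA". The protocol explains the reach of that route: "This means all critical or unexpected adverse effects from medications are reported". It adds known or non-critical side effects for products in their first two years on the market. A further sentence limits CRF entry, from inclusion to withdrawal, to events not related to the patient's medication.

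The other rules carry no medication exception:

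- Section 16.1 defines an AE as any untoward occurrence, "whether or not related to the investigated medical device". The SAE definition in section 16.5 is equally silent on medication.
- Section 16.7 lists "any SAE or SADE" as reportable.
- Section 16.8 makes the site's principal investigator responsible for all SAEs and SADEs there, and states: "All SAEs occurring from accept of the participation to the end of the investigation will be reported". The recipient is the sponsor's medical monitor and the limit is 24 hours.
- Section 16.8 also states: "All events occurring during the trials must be reported in the final report of the investigation". It adds that this includes non-critical events.

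**The concern.** One set of sentences makes reporting depend on the site's view of cause, and the other requires reporting whatever the cause. The protocol does not say which prevails. Two sites could each follow a sentence of section 16.8 and record the same event differently.

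The order of judgement also matters. Section 16.8 makes the medical monitor responsible for ensuring that a possible device cause of an SAE or SADE is carefully evaluated. Under the exclusion, the site's attribution to medication comes first and can stop the event from entering the study record.

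What is at stake is the completeness of the safety data. Section 9.1 summarises AEs descriptively by type, and section 8.6.1 makes the CRF the place where AE type and description are recorded. An event kept out of the CRF is therefore missing from that summary.

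**Working it through.** No arithmetic applies, and the protocol states no figure to reproduce. The check applies each rule to an event that the site attributes to medication.

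| Event attributed to medication | Exclusion and CRF sentences (16.8) | Other rules | Can both be followed? |
|---|---|---|---|
| Serious | Not reported; not in the CRF | 16.7: reportable. 16.8: to the medical monitor within 24 hours, and in the final report | Not as written. The 24-hour duty can be met only if the SAE rule overrides the exclusion, which is not stated |
| Non-serious | Not reported; not in the CRF | 16.8: in the final report. 16.8.1: all events followed regardless of severity | No. No other study source is named from which the final report could take the event |

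**Step 1: scope of the exclusion.** Neither the exclusion sentence nor the CRF sentence is limited to non-serious events. On its face the exclusion covers both rows.

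**Step 2: the favourable reading.** Let the SAE rule override the exclusion. The 24-hour conflict in the first row then disappears. The second row is unchanged, because the final-report rule expressly includes non-critical events. The CRF restriction also remains, so even a serious event reported to the monitor would have no CRF entry.

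**Step 3: the national route.** Section 16.8 sends suspected medication effects through the ordinary duty of medical personnel. Nothing in the text returns those reports to the CRF or the medical monitor. The monitor is also the person who must see that SAEs and SADEs reach the ethics committee, so that path is not supplied either.

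**Step 4: an example from the protocol's own risk statement.** Section 6 expects no known risks, with one exception: some patients may be allergic to the electrode gel. Suppose a patient develops a skin reaction and the site attributes it to medication. The CRF sentence then keeps out an event that may be the one device effect the protocol anticipates. Medication attribution is plausible here, since section 3.3 says that some patients are admitted to improve their treatment.

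**Step 5: what is untouched.** Sensitivity, false detection rate, latency and the PNES measure come from seizure annotations and device detections (sections 3.5.1, 3.5.2 and 10.1). None of them uses AE records.

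**The case against.** The strongest defence is that SAE reporting is unqualified in three places and has its own form, recipient and clock. Section 16.8 also asks for autopsy and medical reports on all deaths, with no medication exception. A coherent reading is that the exclusion governs routine AE recording and the SAE rule stands in full. This is plausible, and it is why loss of a serious event is not certain. But the protocol does not state it, and it leaves the CRF and final-report rules in conflict.

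A second defence is that medication effects are redirected, not discarded. That is correct: critical or unexpected ones are reported nationally. They still leave the study's own record.

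A third is that the monitor's task concerns device causality, not attribution to medication. That also stands. However, the monitor cannot have device causality evaluated for an event that never arrives.

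A reader might infer that the exclusion could hide harm from a missed or late alarm, because section 16.8 makes serious events caused by delayed or wrong treatment reportable. The design does not support this. Alarms are silent, detections are hidden from staff until the admission ends, and usual monitoring is otherwise unchanged (sections 3.2, 3.3, 3.5.1 and 8.1). Nobody acts on an EDDI alarm, so a missed one cannot alter care in this study.

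**Conclusion.** The conflict is real and should be resolved. For non-serious events attributed to medication it holds on any reading. For SAEs it holds unless the SAE rule is taken to override the exclusion, and the text gives no such precedence. The consequence is an AE record that may be incomplete and may differ between sites according to which sentence each follows.

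The size cannot be given. The protocol states no expected number of medication-attributed events. A reader might want to express the effect as a confidence limit on an SAE rate among the roughly 80 planned patients, but any count would be assumed, and section 9.1 plans only a descriptive summary. Nor can the predecessor study's report of no SAEs (section 3.1) serve as a yardstick, since its recording rules are not shown.

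The conclusion assumes that the CRF is the source of the AE summary, as sections 8.6.1 and 9.1 indicate, and that the national reports are not fed back by an arrangement outside this document. The point concerns safety reporting only and does not weaken the performance results.

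**What to change.** Reconcile the sentences in section 16.8 with each other and with section 16.7:

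1. Record all AEs in the CRF whatever the suspected cause, and note that cause with the event. Section 8.6.1 currently lists only AE type and description, so one item would be added.
2. State that the existing 24-hour rule for SAEs applies whatever the suspected cause, so that the medical monitor receives each one before device causality is settled.
3. State that national reporting of medication effects is in addition to study reporting and does not replace it.

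The final-report rule then needs no change, because the CRF would hold the events it asks for. The cost is a wording change, one CRF item and a few more event forms over stays of at most 4 days. No device procedure or performance analysis changes.
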